## 1.0 Background

Combat-related amputations remain one of the most common major disabling war-related injuries from modern armed conflict. Since the beginning of combat operations in Iraq and Afghanistan in 2001, more than 1,300 major lower extremity amputations have been sustained by or performed on US service members and women. Adequate rehabilitation post-amputation enable our nation's heroes to reach their maximum functional recovery and independence. Socket comfort is achieved by appropriately loading and off-loading the residual limb, where optimal biomechanical performance of the prosthesis is achieved by transfer motions of the residual limb without loss or excess motion to the prosthesis. Socket design and fit are critical for successful prosthetic use especially for service members with combat related lower extremity limb amputations. Sub-optimal fit and comfort of the prosthetic system are known to cause rejection of the prosthesis and preference toward other assistive devices such as wheelchairs.

In an effort to maximize socket performance and comfort without adversely affecting residual limb health, a prosthetist custom fits a socket for every patient using plaster wraps or computer aided design. Currently, this process suffers from a lack of quantitative feedback to determine appropriate socket volume, and fit. Prosthetists aim to create a comfortable and intimate socket interface, but current techniques are limited as they rely on anecdotal visual cues along with subjective verbal feedback from the patient. We have optimized and reported limb health outcomes that help provide objective feedback to patient and prosthetist fitting the socket. Although the use of the socket is to ambulate in full weight bearing condition, currently almost all of fittings and plaster casting takes place in a seated non-weight bearing position.

The art of socket fabrication must rely on more objective approaches in the interest of robustness. Attempts have been made to develop a socket fabrication technique that requires little or no prosthetic skill. The clinical models range from all traditional techniques with no use of Computer Aided Design and Manufacturing (CAD/CAM), to full in-house suites of CAD/CAM equipment with extensive utilization, to a simplified office with minimal in-house equipment and minimal fabrication and a near total dependency on central fabrication. Once the digital representation of the residual limb is obtained, software is used to add the modifications that transform the digital shape from an exact mold of the amputated limb, to the shape of a functioning prosthetic socket. An exact mold of the residual limb is not a good socket. The socket must be accurately modified by a skilled prosthetist in areas that can better tolerate the transfer of forces, and the socket must be relieved out away from the residual limb in areas that are less tolerant of force and pressure. These special areas of the socket that require modification are called regions and the process is called rectification. Most CAD/CAM software

packages have templates that will identify these regions and add these modifications in a similar fashion even for different sized and shaped limbs after the prosthetist identifies the correct anatomical landmarks for rectification. One major advantage of automated digital technology is that one could robustly fabricate multiple sockets very efficiently over the early rehabilitation time, and thus keep up with the changing shape and volume of the residual limb during the first 12 to 18 months following amputation.

Achieving a comfortable and functional relationship between an amputee and their prosthetic socket is critical to the success of the prosthesis. Therefore, the prosthetic socket and interface are the most significant component for the overall rehabilitative success of the prosthesis. Over 75% of patients with lower-limb prosthetics have skin problems. Ulcers or pressure sores, are the most common skin conditions in prosthetic users and can vary in size and magnitude requiring prolonged recovery time out of the prosthesis, a new socket fitting and sometimes surgical interventions. To preserve and promote residual limb health, one key factor is to maintain the functional integrity of the skin, perfusion and oxygenation. Functional integrity of the skin is a critical determinant of ulcer formation. Our group and others have demonstrated that trans-epidermal water loss (TEWL) measures the functional integrity of the skin, a reliable early marker of skin ulceration. Breach in physical integrity of the skin is preceded by breach of functional integrity of skin as measured by elevated TEWL. Previous research lends credence to the hypothesis that the residual limb skin is susceptible to breakdown and ulceration in response to repeated stress from use of prosthesis.

Micro-vasculopathy is known to complicate limb health. We reported the first post-processing of binary raw data from a high-resolution LSCI camera. This tool is valuable in determining micro-vasculopathies compromising limb health following use of a specific type of socket. These studies described above clearly demonstrate value of in-socket and out-of-socket non-invasive unique measurement tools developed by our group for monitoring limb health of residual limb in sockets. These studies also demonstrate experience of our group in performing such clinical studies in this area.

## **2.0     Objective(s)**

### **2.1     Primary Objective**

Evaluate the efficacy of the Symphonie Aqua Digital System (SADS) and the health of the residual limb outcomes compared to non-weight bearing standard of care sockets.

## **2.2 Secondary Objective**

The secondary objective includes

- i) pressure inside the socket
- ii) assessment of functional outcomes
- iii) patient reported (PR) outcomes

We hypothesize that digital shape capture of a residual limb using EMTS under full weight bearing environment will provide accurate anatomical shape of the residual limb, improved fit of the prosthetic socket; thus, preserving limb health and volume during activities of daily living (ADL). Such accuracy will improve limb health and rehabilitation outcomes following amputation.

## **3.0 Aims**

### **3.1 Aim 1**

Evaluate the efficacy of the SADS on long-term limb health of the residual limb outcomes (TEWL and LSCI measurements) compared to traditional non-weight bearing shape capture techniques.

### **3.2 Aim 2**

Long-term assessment of functional outcomes, and patient reported (PR) outcomes in response to use of SADS.

## **4.0 Eligibility Criteria**

### **4.1 Inclusion Criteria**

- Ages 18 and above
- Unilateral trans-tibial amputees
- Ambulate at a K3 level or higher
- At least 3 months post-amputation per physician discretion
- Trans-tibial limb length greater than 4.5 inches in length
- Able to follow directions and independently give informed consent
- Must be able to ambulate without assistance

#### **4.2 Exclusion Criteria**

- Age < 18 years
- Conditions that prevent wearing a prosthetic socket
- Soc Socket made with weight bearing system
- Cognitive deficits or mental health problems that would limit ability to consent and participate fully in the study protocol
- Women who are pregnant or who plan to become pregnant in the near future
- Weight > 280 lbs

### **5.0 Study Design**

This is a 16-week pilot, prospective, cross over study to meet the objective of the study where the novel EMTS based digital weight bearing system will be compared to SoC non-weight bearing socket design for improving limb health and functional outcomes post 6 weeks use. The subject (n=12) lower extremity unilateral trans-tibial subjects will participate in both study arms sequentially: Arm 1 (SoC- non-weight bearing): and Arm 2: EMTS based shape capture in full weight bearing using (SADS, Symphonie Aqua Digital System, Romedis GmbH).

#### **5.1 Enrollment**

The subject (n=12) lower extremity unilateral trans-tibial subjects will begin the study on Arm 1 (SoC- non-weight bearing (Socket A) : and then move to Arm 2: EMTS based shape capture in full weight bearing using (SADS, Symphonie Aqua Digital System, Romedis GmbH, Socket B).

#### **5.2 Study Procedures**

**Study Visit 1a-c (Initial Evaluation/Fitting; Weeks 0-6):** Immediately post-enrollment, socket shape capture will be completed with Digital and non-digital weight bearing Aqua systems. Baseline measurement for SoC will be performed. The following baseline measurements will be performed for SoC Socket (Socket A) at this first visit:

- TEWL measurement
- Laser Speckle Flowmetry (LSI)
- In-Socket Sensors
- Motion Capture Analyses
- 6 Minute Walk Test (6MWT)
- Timed Up-and-Go (TUG)
- Houghton Scale

- **Socket Comfort Score**
- **Veterans RAND 36-Item Health Survey**

The fitting of the digital and non-digital weight bearing sockets will continue for up to 4-6 weeks to ensure proper fitting of the weight bearing socket and comfortability during this time the subjects will continue to use their SoC socket A.

**Study Visit 2 – SoC final visit (week 6 +/- 2 Weeks):** Participants will return to the hospital. Participants will be asked to wear clothing that is comfortable for them while they may be participating in physical activity prior to attending the visit. Study members will offer specific guidance on study if necessary. If they do not have any comfortable clothing, they will be asked to speak with research personnel. Research personnel will provide them with the appropriate clothing if they are unable to bring any during this visit. The following procedures will be performed during this visit with their Socket B.

- **TEWL measurement**
- **Laser Speckle Flowmetry (LSI)**
- **In-Socket Sensors**
- **Motion Capture Analyses**
- **6 Minute Walk Test (6MWT)**
- **Timed Up-and-Go (TUG)**
- **Houghton Scale**
- **Socket Comfort Score**
- **Veterans RAND 36-Item Health Survey**

At this visit, the definitive **socket B** will be ready & fitted; the measurements in this visit will serve **as the baseline visit values for Socket B**; End of this visit the participants will start using the Socket B for next 6 weeks Study members will offer specific guidance on study as necessary.

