- **Veterans RAND 36-Item Health Survey:** Is a brief, generic, multi-use, self-administered health survey comprised of 36 items. The instrument is primarily used to measure health-related quality of life, to estimate disease burden and to evaluate disease-specific impact on general and selected populations.
- The fitting procedures and/or techniques of the research socket will mirror the techniques of the subject's primary prosthetist used to fabricate their SOC socket. The only difference is the method of capturing the shape of the residual limb: weight-bearing vs non-weight-bearing.
- There may be risks that we don't know about at this time. While the goal of this project is to create a more comfortable prosthesis, it is possible that subjects will experience discomfort such as perspiration, dry skin, rash, itching, irritation, blisters, high pressure in the socket, looseness in the socket, and mechanical rubbing which may cause ulcerations.

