## **9.0 Study Withdrawal/Discontinuation**

Patients will be informed during the informed consent process (in writing and verbally) that they are free to withdraw from the trial at any time. The investigator may exercise his medical judgement to terminate a patient's participation in the trial due to clinically relevant changes in any clinical or laboratory parameter. The Sponsor-Investigator also reserves the right to discontinue/terminate the trial at any time.

Discontinuation criteria for individual subjects include: (1) Non-compliance with the inclusion/exclusion criteria, (2) treatment non-compliance, such as use of another socket prosthesis, (3) withdrawal from the study due to reasons not related to the treatment, (4) prosthetic socket becomes uncomfortable.

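### Weight-bearing socket fitting runs inside the Socket A period with no set interval before Visit 2, so the Visit 2 TEWL and laser speckle readings may not reflect Socket A alone

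*Combined protocol and SAP*

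**What the plan says.** Everything here is in the combined protocol and SAP.

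- **Overlap.** Section 5.2 labels Visit 1a-c "Initial Evaluation/Fitting; Weeks 0-6". It says "The fitting of the digital and non-digital weight bearing sockets will continue for up to 4-6 weeks to ensure proper fitting", and adds that "during this time the subjects will continue to use their SoC socket A". The fitting weeks are thus also the Socket A weeks.
- **Visit 2.** Section 5.2 heads it "SoC final visit (week 6 +/- 2 Weeks", that is, weeks 4 to 8. It then says: "The following procedures will be performed during this visit with their Socket B". The values are to serve as the Socket B baseline.
- **Start of Socket B.** "End of this visit the participants will start using the Socket B for next 6 weeks".
- **Sequence.** Section 5.1 puts all 12 subjects on Socket A first and Socket B second.
- **Analysis.** Section 10.0 makes TEWL the primary endpoint and laser speckle imaging a secondary endpoint of Aim 1. Carryover appears only in the model for functional and patient-reported measures.

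Sections 5.2 and 6.0 give no minimum time between the last fitting and Visit 2, no limit on wear during fitting, no fitting log and no rest rule before TEWL or laser speckle.

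**The concern.** During the Socket A weeks the residual limb may also be loaded in weight-bearing sockets that are still being adjusted, possibly shortly before Visit 2. Section 1.0 presents TEWL as an early marker of skin breakdown and describes residual-limb skin as vulnerable to repeated prosthetic stress. The risk text in Section 5.2 lists irritation, looseness, high pressure and "mechanical rubbing which may cause ulcerations" among possible discomforts. On the protocol's own reasoning, fitting exposure could plausibly move the primary endpoint.

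If it raised TEWL at Visit 2, part of any fall by Visit 3 would be recovery from fitting. If it lowered TEWL, a real benefit would be partly hidden. This applies whether Visit 2 closes the Socket A period or opens the Socket B period, because either use puts the Visit 2 value into the socket comparison. The pilot is meant to inform the sample size of a later study, so a biased paired change would carry forward.

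**Working it through.** **1. Timeline.** Inputs from Section 5.2: fitting starts at week 0 and ends between weeks 4 and 6; Visit 2 falls at week 6 +/- 2.

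Gap = week of Visit 2 - week in which fitting ends.

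| Fitting ends | Visit 2 at week 4 | Visit 2 at week 6 | Visit 2 at week 8 |
|---|---|---|---|
| Week 4 | 0 | 2 | 4 |
| Week 5 | -1 | 1 | 3 |
| Week 6 | -2 | 0 | 2 |

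At the nominal Visit 2 the gap is 0 to 2 weeks; over the whole window it is -2 to +4 weeks. A negative gap means fitting is still under way. Since the definitive Socket B should be ready at Visit 2, the practical lower end is probably about 0. Either way, no positive interval is guaranteed.

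**2. Which socket Visit 2 describes.** The heading makes it the last standard-of-care visit. The procedures are assigned to Socket B. Regular Socket B use starts only when the visit ends. Taken together, no reading is clearly designated as the end-of-period Socket A value. A fitting-free interval before the visit would not isolate Socket A if Socket B is worn for the readings.

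**3. Possible size (illustration only).** The plan gives no SD, effect size or power, so there is no figure to reproduce. It also names no specific test for TEWL; a paired t-test of Visit 3 minus Visit 2 is my assumption, with n = 12, 11 degrees of freedom and two-sided 5%.

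- 95% CI half-width = t(0.975, 11)/sqrt(12) = 2.201/3.464 = 0.635 SD of the paired difference.
- If fitting raises the Visit 2 reading by d SDs, the change shifts by -d. With no true socket effect, the rejection rate comes from the noncentral t with noncentrality d x sqrt(12):

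| Assumed d | Noncentrality | Rejection rate |
|---|---|---|
| 0.1 | 0.346 | 6.2% |
| 0.2 | 0.693 | 9.7% |
| 0.3 | 1.039 | 15.8% |
| 0.5 | 1.732 | 35.3% |

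- In the other direction, 12 pairs give 80% power at a standardized difference of 0.889. If a share f of a Socket B effect were already present at Visit 2, the observable difference would be 0.889 x (1 - f). For f = 10%, 25% and 50% that is 0.800, 0.666 and 0.444, with power of about 71%, 56% and 29%.

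The documents supply no value for d or f. Any bias of the same size would give the same rates, so the tables show sensitivity and are not evidence that a bias exists.

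**The case against.** The strongest reply is that a custom socket has to be fitted before use, that Socket A remains the everyday socket throughout, and that fitting may mean a few short supervised sessions. No section says that brief fittings alter TEWL or perfusion days later: Section 1.0 speaks of repeated stress from prosthesis use, and the risk list gives only possible discomforts. The case report forms are not in the documents and may record fittings. All of this stands, and it limits the conclusion to a possible effect.

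Three stronger readings are tempting but unsupported.

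- *Visit 2 is contaminated by fitting.* A reader might infer this from the overlap. The documents do not describe the amount of fitting wear, and Socket A use continues, so contamination is not shown.
- *The schedule breaches its own compliance rule.* Section 9.0 lists "treatment non-compliance, such as use of another socket prosthesis" as a ground for discontinuation. Fitting directed by the protocol is not naturally read as non-compliance; if anything, the rule limits everyday wear of the test socket in weeks 0-6.
- *The planned carryover term was meant to deal with this and fails.* Section 10.0 confines that term to functional and patient-reported measures. None is planned for TEWL or laser speckle, and with one fixed sequence carryover could not be separated from socket and period effects in any case.

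The reply does not supply an interval, a limit on wear or a clear socket assignment at Visit 2. The contralateral TEWL reference does not help either, since only the residual limb is fitted.

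**Conclusion.** The concern holds in a limited form. Fitting overlaps the Socket A period, no fitting-free interval before Visit 2 is assured, and the protocol neither limits fitting wear nor requires it to be logged. Visit 2 TEWL and laser speckle readings may therefore not reflect Socket A alone. Size and direction are unknown; the 6% to 35% false-positive rates and the power losses rest on assumed shifts and an assumed paired t-test, in a pilot with no stated power. The more certain defect is the conflict within Section 5.2 over which socket the Visit 2 measurements describe. It must be reconciled first, because the meaning of any interval depends on it. This is a cheap improvement and does not by itself invalidate the design.

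**What to change.** 1. **Section 5.2, Visit 2.** State which socket each reading belongs to. Take the end-of-period Socket A TEWL and laser speckle readings before Socket B is put on, and after a fitting-free interval whose length the sponsor chooses.
2. **Fitting log.** Record the date, the socket and the minutes worn at each fitting. If this exposure is not recorded at the time, it cannot be reconstructed later.
3. **Visit 1 and Section 10.0.** Take the Visit 1 TEWL and laser speckle readings before weight-bearing shape capture. Section 5.2 describes shape capture first and does not fix the order, and Section 14.0 describes it as full weight bearing under hydrostatic pressure. Then add Visit 3 versus Visit 1 as a sensitivity contrast, since Visit 1 is the only reading clearly assigned to Socket A. Note its weakness: it spans about 12 weeks (12 - 0) against 6 (12 - 6) for Visit 3 versus Visit 2, so in a fixed A-then-B sequence it is more exposed to period effects. It should accompany the Visit 2 comparison and not replace it.

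**Cost.** Visit 2 may move by a few days, within its existing +/- 2 week window. Beyond that, the cost is some wording on measurement order, a short log and one extra contrast from visits already planned.

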**Study Visit 3 (week 12 +/- 2 Weeks):**

- Participants will return to the hospital. They should wear clothing that is comfortable for them while you may be participating in physical activity. Study members will offer specific guidance on study if necessary. The following procedures will be performed during this visit with their test Socket B following 6 weeks of use.
- **TEWL measurement**

- **Laser Speckle Flowmetry (LSI)**
- **In-Socket Sensors**
- **Motion Capture Analyses**
- **6 Minute Walk Test (6MWT)**
- **Timed Up-and-Go (TUG)**
- **Houghton Scale**
- **Socket Comfort Score**
- **Veterans RAND 36-Item Health Survey**

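### Visit 2 is titled as the end of the standard-of-care period but orders its tests in Socket B, and the plan never settles which socket the Visit 2 values belong to

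*Combined protocol and SAP*

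**What the plan says.** All 12 participants take the two sockets in the same order. Under 5.1 they "will begin the study on Arm 1", the standard-of-care (SoC) Socket A, and then move to Socket B, made from the weight-bearing shape capture. Section 5.0 frames the comparison of the two as one "for improving limb health and functional outcomes post 6 weeks use".

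Section 5.2 then sets out three visits, each with the same nine procedures.

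- Visit 1: "Baseline measurement for SoC will be performed", and the list that follows is assigned to Socket A. While Socket B is being fitted, "during this time the subjects will continue to use their SoC socket A".
- Visit 2: the heading is "SoC final visit (week 6 +/- 2 Weeks". The body says "The following procedures will be performed during this visit with their Socket B", and that the measurements serve "as the baseline visit values for Socket B". Participants begin using Socket B at the end of the visit.
- Visit 3: the procedures are "performed during this visit with their test Socket B following 6 weeks of use".

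The Study Calendar (6.0) has one mark per procedure at each visit and names no socket. Section 10.0 evaluates functional outcomes at baseline and after 6 weeks of socket use, and plans a mixed model for the effect of socket type on functional and patient-reported composites. It does not say which visit supplies which socket's value.

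**The concern.** The heading makes Visit 2 the closing assessment of the Socket A period. The body makes it the opening assessment of Socket B, worn in Socket B. For a test whose result depends on the socket being worn, a single set of measurements cannot describe performance in both sockets.

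At stake is the SoC side of the comparison for pressure, function and comfort, which fall under the secondary objectives in 2.2. If staff follow the body text, no test in Socket A is ordered after the 6 weeks of on-study Socket A use, and a test not done in that socket on that day cannot be recovered later. If some visits follow the heading and others the body, the Visit 2 column of the data would mix two sockets under one label. The pilot exists to provide preliminary data for sizing a later study, so an unclear comparator would carry forward.

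**Working it through.** The plan gives no figure to reproduce, and no formula applies. The check sets the statements side by side and asks what each reading leaves available.

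**Step 1. What each visit supplies (section 5.2).**

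| Visit | Nominal week | Socket for the tests | Role of the values |
|---|---|---|---|
| 1 | 0 (assumed for the baseline tests) | A | Socket A baseline |
| 2, by heading | 6 | A implied | End of Socket A period |
| 2, by body | 6 | B stated | Socket B baseline |
| 3 | 12 | B stated | Socket B after 6 weeks |

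**Step 2. Which procedures depend on the socket worn.** From the procedure details in 5.2:

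- Five are socket-worn: in-socket pressure (sensors sit in the socket), motion capture (walking with those sensors), 6MWT, TUG, and the Socket Comfort Score (rated for the socket at the moment of scoring).
- Two are read on the limb: TEWL and laser speckle.
- Two are questionnaires: Houghton and RAND-36. No recall period is given for either.

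The split is 5 + 2 + 2 = 9 procedures.

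**Step 3. Body text followed.** The socket-worn tests exist for Socket A at Visit 1, Socket B at Visit 2 and Socket B at Visit 3. There is no Socket A value after the 6-week SoC period. The only Socket A comparator is Visit 1. From the stated windows, Visit 3 is at 12 ± 2, so it lies 12 − 0 = 12 weeks after Visit 1 (10 to 14).

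**Step 4. Heading followed.** The socket-worn tests exist for Socket A at Visit 1, Socket A at Visit 2 (after 6 ± 2, so 4 to 8, weeks of on-study wear) and Socket B at Visit 3. The 6-week value is available for both sockets. The Visit 2 values could also act as the pre-switch baseline for the Socket B period. What does not exist is a value worn in Socket B at the start of that period.

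**Step 5. The other four procedures.** At Visit 2 the limb has had about 6 weeks in Socket A. One TEWL or laser speckle reading can therefore be both the SoC 6-week outcome and the pre-Socket-B baseline, provided it is taken before any activity in Socket B. The two measures are listed first, but no order is stated, and the only label given is Socket B baseline. Houghton and RAND-36 can serve in the same way if they are assumed to reflect the preceding weeks.

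**Step 6. Does another section settle it?** The calendar does not name the socket. Section 10.0 does not map visits to sockets. Section 5.0 sets the 6-week comparison, which favours the heading, but it does not override the explicit instruction in the body of 5.2.

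**The case against.** The strongest reply is that the body text is operative and clear: it names Socket B twice, and the heading may only mark the visit at which SoC use ends. A coordinator can carry that out, so it would be too strong to infer that Visit 2 cannot be performed as written. This stands. But on that reading the Socket A 6-week tests are absent, which does not fit the comparison described in 5.0.

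A second reply is that in a fixed A-then-B sequence the end-of-A values are a natural pre-switch baseline for B. If only the words assigning the tests to Socket B are a slip, the heading and the baseline sentence agree. This also stands. A reader might infer that a quarter of the socket-worn data is missing however the text is read, because two sockets at two times make four sets and only three are scheduled. The documents do not support that count, since they do not require the Socket B baseline to be a separate set worn in Socket B.

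Third, Visit 1 may be an adequate SoC value. Participants continue with Socket A, and 5.2 refers to the subject's own prosthetist having made it, so it may already be in established use. That is possible, but prior wear is neither stated nor recorded, and section 10.0 does not name Visit 1 as the comparator.

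Fourth, the reach into the planned analysis is limited. The mixed model in 10.0 covers only functional and patient-reported measures. No analysis is given there for in-socket pressure or motion capture, and the walk test named is 2MWT, not the scheduled 6MWT. Of the five tests, TUG and presumably the Socket Comfort Score feed the model; the walk test does so only if 2MWT is a slip.

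**Conclusion.** The inconsistency is real, sits within one paragraph of the current text, and is not resolved elsewhere. Its extent is five of the nine Visit 2 procedures in a 12-participant pilot. On the literal body text they lack a Socket A value at 6 weeks, and the comparison falls back on a Visit 1 value about 12 weeks before Visit 3. On the heading they lack only a Socket-B-worn starting value.

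A reader might infer that the primary endpoint is compromised. It is not: TEWL is a skin reading, and it needs a second label and a stated measurement order, not a new measurement. Nor can the direction or size of any bias from using Visit 1 be worked out, because the documents give no variability or time trend.

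The conclusion assumes that the Visit 1 baseline tests take place at week 0 and, for Houghton and RAND-36, that answers reflect the preceding weeks. Because the affected outcomes are secondary and the remedy is mostly wording, this is an internal inconsistency that should be fixed before Visit 2 data are collected, not a defect that invalidates the study.

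**What to change.** Reconcile the Visit 2 heading and body in 5.2, and carry the result into 6.0 and 10.0.

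- **Limb readings and questionnaires.** At Visit 2, take TEWL, laser speckle, Houghton and RAND-36 before Socket B is put on. Label them both as the SoC 6-week outcome and as the pre-Socket-B baseline.
- **Socket-worn tests.** Do the five tests in Socket A and label them as the SoC 6-week outcome. Either use them as the pre-switch baseline as well or, as an option, repeat them in Socket B at the same visit.
- **Calendar and analysis.** Name the socket for each visit in 6.0. State in 10.0 which visit supplies each socket's baseline and 6-week value. Record how long Socket A was worn before enrolment.

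Cost: wording changes and one wear-duration field, with no added visit or participants. Without the repeat, there is no starting value worn in Socket B. With it, Visit 2 is longer and fatigue or test order may affect the second set. Neither choice separates socket from period: every participant goes from A to B, so that confounding remains and should be acknowledged when the results are reported.
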